9.12.2 Prohibited Therapies

The following co-medication/therapies are not allowed during participation in the study:

- EGFR targeting agents apart from randomly assigned study medication until end of treatment.
- Any other immunotherapy until end of treatment.
- Any anti-cancer treatment other than described in this protocol until end of treatment.
- Ongoing regular doses of hydrocortisone and steroids (except for topical/inhaled) other than corticosteroids used for precaution of IRR.
- Immunosuppressive agents until end of treatment.
- Radiation therapy (except palliation of existing bone metastasis pain).
- Erythropoietin (Epo).
- Other medications that are contraindications to 5-FU and cisplatin or carboplatin respectively as per SmPC 4.3 “Contraindications” and 4.5 “Interaction with other medicinal products and other forms of interaction” (see Appendices F, G, H).

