10.3.1.2 Assessment of Secondary Efficacy Endpoints

Tumor assessments performed by the investigator and by independent centralized reading as described in detail above will also be used for evaluation of secondary efficacy endpoints.

Progression-free Survival assessed by Centralized Read

Tumor images to determine PFS as assessed by independent centralized reading will be evaluated as described in detail in Section 10.3.1.1.

Objective Response Rate and Duration of Response

Objective response rate is the portion of patients with a tumor size reduction of a predefined amount for a minimum time period and it is defined as the sum of partial responses and complete responses. Response duration is measured from the time of initial response until documented tumor progression.

The investigator and independent centralized reader will evaluate whether complete response (CR), partial response (PR), stable disease (SD) or progressive disease (PD) has occurred, according to the criteria presented in Appendix C:

Best Overall Response Rate

The best overall response rate is the best response (CR, PR or SD) recorded per patient from the start of the treatment until disease progression/recurrence. Separate rates per CR, PR or SD as best response will be evaluated.

Clinical Benefit Rate

The clinical benefit rate is the portion of patients with an objective response or stable disease.

Overall Survival

The overall survival is defined as the duration of time from randomization to the time of death. The patients will be followed up by monthly phone calls until death or for a maximum duration of 24 months after randomization of the last patient for assessment of OS.

Time to Treatment Failure

Time to treatment failure is defined as the time from randomization to treatment discontinuation for any reason, including disease progression, treatment toxicity, patient preference, or death.

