##### Follow-up

A Safety Visit must be performed 28 (+2) days after the last administration of the study drug for all randomized patients. In case of treatment discontinuation due to reasons other

than disease progression, patients will stay on the regular study schedule until disease progression is documented and will then attend a Final Examination Visit. In case of treatment discontinuation due to disease progression, the Safety Visit is identical to the Final Examination Visit.

After the Final Examination, patients will be followed-up by quarterly phone calls until death or for a maximum duration of 24 months after randomization of the last patient for assessment of overall survival.

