Variable Name	Computation Methods, Notes, or Equation(s)		
PFSp  (primary definition)	= Earliest date of progression or death - date of randomization + 1 The earliest date of PD will be used irrespective of PD confirmation		
	Finding	Date of PD of Censoring	Outcome
	No PD or death	Pre and post-baseline imaging done: Date of last imaging	Censored
		No baseline or no post-baseline imaging done: Date of randomization	Censored
	Progression/death documented after a new anticancer treatment has started PD at scheduled visit PD between scheduled visits	Date of last imaging prior to new anticancer treatment Date of imaging Date of imaging	Censored Event Event
PFSs  (sensitivity definition)	= Earliest date of progression or death - date of randomization + 1 The earliest date of PD will be used irrespective of PD confirmation		
	Finding	Date of PD of Censoring	Outcome
	No PD or death	Pre and post-baseline imaging done: Date of last imaging	Censored
		No baseline or no post-baseline imaging done: Date of randomization	Censored
	Progression/death documented after a new anticancer treatment has started PD at scheduled visit PD between scheduled visits*	Date of last imaging prior to new anticancer treatment. Date of imaging Date of next scheduled visit	Censored Event Event
	PD after 2 or more missing scheduled visits	Date of last imaging prior to first missing visit.	Censored
	Death up to 16 weeks (112 days) after last imaging Death later than 16 weeks (112 days) after last imaging	Date of death Date of last imaging	Event Censored
Best overall response	Best modified irRC classification (CR, PR or SD) as assessed by the investigator or by the independent centralized review		

(rates) (BO(R))	SD: follow-up measurements must have met the SD criteria at least once after randomization at a minimum interval of 8 weeks.
Objective response (rate) (OR(R))	Best response of CR or PR
Clinical benefit (rate) (CB(R))	Best response of CR or PR or SD. SD: follow-up measurements must have met the SD criteria at least once after randomization at a minimum interval of 8 weeks

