Duration of response	= Date of first progression or death after initial response - date of first response + 1 Date of disease progression is defined as the date of imaging showing disease progression. Date of response is defined as the first date of imaging showing CR or PR. If no progression or death is observed after initial response, the duration of response will be censored at the last date of tumor assessment.
Duration of CR	= Date of first progression or death after initial response - date of first CR + 1 Date of disease progression is defined as the date of imaging showing disease progression. Date of CR is defined as the first date of imaging showing CR. If no progression or death is observed after initial CR, the duration of CR will be censored at the last date of tumor assessment.
Other variables	
Overall survival (OS)	Date of death – date of randomization + 1 If no death is observed, OS will be censored at the last date known to be alive.
Time to treatment failure (TTF)	Date of treatment discontinuation for any reason (including disease progression) as assessed by investigator, treatment toxicity, patient preference, or death) – date of randomization If no treatment discontinuation is observed, TTF will be censored at the date of last study treatment.
Body surface area (BSA)	$BSA [m^2] = \text{SQRT}((\text{weight [kg]} \times \text{height [cm]}/3600))$
Number of combination treatment cycles	Number of treatment cycles with full combination treatment (3 doses of CetuGEX™/cetuximab, one dose of cisplatin/carboplatin, 4 doses of 5-FU) Only cycles in which all planned medication has been given will be counted as a full cycle. Dose reductions will however not prevent a cycle to be counted as full.
Overall treatment duration [weeks]	(Date of last treatment administration – date of first treatment administration) + 1 for CetuGEX™/cetuximab
Treatment duration [weeks] during combination treatment	(Date of last treatment administration within a combination cycle – date of first treatment administration) + 1 for CetuGEX™/cetuximab
Treatment duration [weeks] in maintenance phase	(Date of last treatment administration – date of first treatment administration after last Day 15 administration in combination treatment phase) + 1 for CetuGEX™/cetuximab

Total doses [mg]	Sum of actual doses administered for CetuGEX™/cetuximab cisplatin/carboplatin and 5-FU
------------------	--

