*Prior and concomitant medication:* All medication will be coded using the WHO-DRUG dictionary September 2013 edition (or newer). Incidences of prior and concurrent medications will be summarized by ATC level 2 and ATC level 4 if applicable.

Concomitant medication is defined as a medication other than study drug that was administered during the treatment period. The treatment period is defined as the time from day of first treatment to the EOS visit. Medication that has been classified as

premedication will be analyzed separately. Additionally the number of corticosteroids applications per patient will be analyzed.

Prior medication is defined as medication which was discontinued before start of study treatment. Medication which was started after the treatment period will be listed but not analyzed otherwise.

If the start date and stop date of medication are partially or completely missing, a medication will be assumed to be concomitant if it cannot be definitely shown that the medication was not administered during the treatment period. Missing dates will not be replaced.

Thus, the following approach will be taken for exclusion from concomitant medication because of discontinuation before start of treatment:

- If stop day is missing but month is complete, medication will only be excluded from concomitant medication if stop month is before month of treatment start.
- If stop day and month are missing but year is complete, medication will only be excluded from concomitant medication if stop year is before year of treatment start.
- If stop date is completely missing, medication will not be excluded.

For exclusion from concomitant medication because of late start after end of treatment period:

- If start day is missing but month is complete, medication will only be excluded from concomitant medication if start month is after end month of treatment period.
- If start day and month are missing but year is complete, medication will only be excluded from concomitant medication if start year is after end year of treatment period.
- If start date is completely missing, medication will not be excluded from concomitant medication.

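### SAP 7.2 does not exclude tumor assessments made after new anticancer treatment from best response, ORR, clinical benefit or duration of response, so a later regimen's effect can be credited to the randomized antibody

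*SAP*

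**What the plan says.** The derivation table in SAP Section 7.2 gives best overall response as "Best modified irRC classification (CR, PR or SD) as assessed by the investigator or by the independent centralized review". Objective response is then "Best response of CR or PR". Clinical benefit adds stable disease, provided the criteria were met at least once at a minimum interval of 8 weeks. None of the three rows states a closing date.

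For duration of response the same table says "If no progression or death is observed after initial response, the duration of response will be censored at the last date of tumor assessment". The row for complete responses is handled in parallel. Neither row mentions new anticancer treatment.

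The PFSp and PFSs rows do. Progression or death documented after a new anticancer treatment is censored at "Date of last imaging prior to new anticancer treatment".

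Two other rules matter. Patients who stop treatment for reasons other than progression are still scanned: "patients will stay on the regular study schedule until disease progression is documented" (SAP 3.1, Follow-up; Protocol 7.1.1 and 8.3 agree). And the list of prohibited therapies in Protocol 9.12.2 reads "Any anti-cancer treatment other than described in this protocol until end of treatment", so it no longer applies once study treatment has ended.

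**The concern.** The SAP foresees patients who change therapy before progression, but deals with them only for PFS. SAP 7.1 bases response and benefit rates on the observed assessments. Taken literally, these include scans made under a later regimen. ORR and CBR would then partly measure what was given after the antibody.

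These rates feed the chi-square tests and logistic models of SAP 9.2.2. CBR also feeds the covariate models of 9.3.2 and the exposure-response models of 9.3.3. If switching before progression differs between arms, the comparisons shift for a reason unrelated to the randomized antibodies. For duration of response, time on the later regimen and a death after it are both attributed to the study arm.

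**Working it through.** **1. The plan's own figure.** The documents state no rate or power for response. The only sizing figure is 192 PFS events. With d = 4(1.960 + 0.842)²/(ln HR)², HR = 5.6/8.4 = 0.667 gives 191 events and HR = 0.67 gives 196, so 192 reproduces. It does not depend on the rows discussed here.

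**2. The rows side by side (SAP 7.2).**

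| Variable | Stops at progression? | Rule for new anticancer treatment? |
|---|---|---|
| PFSp, PFSs | Progression is the event | Yes, if progression or death follows it |
| BOR | Not in the SAP row; yes in Protocol 10.3.1.2 and Appendix C | None |
| OR, CB | Inherited from BOR | None |
| Duration of response, duration of CR | Progression is the event | None |

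**3. Can the situation arise?** Yes. Protocol 9.9 requires withdrawal from antibody treatment after a grade 3 or 4 allergic/hypersensitivity reaction. Under Protocol 8.3, patients withdrawn from treatment before progression remain on schedule, except for noncompliance or where this would conflict with their interest. From then on, Protocol 9.12.2 no longer bars another regimen.

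**4. Two hypothetical patients.**

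- *Patient A* stops after the first infusion, starts another regimen at week 4 and has a first PR at week 12. The rows as written give a responder and a clinical benefit. If week 12 shows stable disease instead, the patient is still a clinical benefit: scans fall at weeks 6, 12 and 18, and week 12 is the first scheduled scan beyond 8 weeks. In PFSp the patient is censored at the last scan before the switch only if progression or death follows. Otherwise censoring is at the last imaging, after the switch.
- *Patient B* has a PR at week 6 on study treatment, stops for toxicity, switches before week 12 and later dies without progression. Duration of response is date of death minus date of the week 6 scan + 1, an event. PFSp censors the same patient at the week 6 scan.

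**5. Scale, on assumptions that are not in the documents.** Take 240/2 = 120 patients per arm.

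- One patient wrongly counted: 1/120 = 0.83 points.
- Suppose 5–15% of an arm switch before progression, and 10–40% of those first respond or first stabilise afterwards. The share affected runs from 0.05 × 0.10 = 0.5 points (0.6 patients) to 0.15 × 0.40 = 6 points (7.2 patients). Because stabilisers are included, this is a range for CBR within one arm. The effect on ORR can be no larger.
- Between arms, for ORR: with 10% v 5% switching and 30% responding in each, the spurious difference is 0.30 × (0.10 − 0.05) = 1.5 points. At an ORR of 40% the standard error of the difference is √(2 × 0.4 × 0.6/120) = 6.3 points, so the shift is 1.5/6.3 = 0.24 standard errors.
- An extreme case: 6 patients credited in one arm only (6/120 = 5.0 points), with equal true rates. The chance of a significant result in that arm's favor rises from 2.5% to about 12–15%, for true rates between 20% and 50%.

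**The case against.** A reader might infer that best response is not cut off at first progression at all. The documents do not support that. Protocol 10.3.1.2 defines it as "recorded per patient from the start of the treatment until disease progression/recurrence", Appendix C says the same, and SAP Section 12 declares no departure from the protocol. ORR and CBR derive from best response and inherit the limit. What remains is a failure to restate, which matters a little because the SAP derives response from three reads (investigator irRC, central irRC, central RECIST 1.1). Investigator irRC progression governs discontinuation, so central RECIST progression can come earlier while scans continue. Neither document says which read's progression closes best response for each read.

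The stronger defense concerns the window. SAP 2.2.1 and 9.2.2 tie the rates to combination treatment or to treatment including maintenance, and SAP 7.2 describes assessments as made in those two phases. A patient on another regimen is in neither. The only SAP definition of the term, "The treatment period is defined as the time from day of first treatment to the EOS visit", is in Section 8.3 and was written to classify concomitant medication; elsewhere SAP 7.2 ends treatment duration at the last administration. This stands to the extent that the text can be read as excluding the scans in question, so it would be too strong to say the plan prescribes crediting them. It does not close the gap. Scans outside both phases exist by design, and no end date for the response window is given.

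It is also fair to say that only secondary and exploratory analyses are touched.

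**Conclusion.** The point holds as a correctable omission. Followed literally, the SAP rows can credit a later regimen's response or stable disease to the randomized antibody. They also treat death after a switch as a duration-of-response event where PFSp censors.

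A reader might go further and infer that ORR or CBR is biased toward a particular arm. The documents do not support this: they give no switching rate and do not establish which arm would have more treatment stops before progression. On the assumed inputs, the between-arm effect on ORR is small in the moderate scenario (1.5 points against a standard error of 6.3) and material only if the affected patients are concentrated in one arm. Primary PFS has its own rule and is unaffected. This is a cheap improvement, not a threat to the trial's main conclusion.

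**What to change.** Before database lock, add to the BOR, OR and CB rows of SAP 7.2, separately for investigator irRC, central irRC and central RECIST 1.1:

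> Only post-randomization assessments up to and including that read's first PD and before the start of any new anticancer treatment are used; patients with no such assessment count as no response/no benefit.

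Derive the start of response from the same assessments. Censor duration of response and duration of CR at the last imaging before new anticancer treatment whenever that treatment starts before PD, whether or not PD or death follows. Copying the PFSp row would not be enough, because it acts only when PD or death is documented after the switch.

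The cost is a few lines of SAP text and one date filter. PFSp already needs the start date of new treatment, and SAP 7.1 already counts patients without sufficient data as non-responders. The small downside is that a few patients may move from responder to non-responder and some response durations are censored earlier.

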During the combination treatment phase, all randomized patients will receive 5-FU as continuous intravenous infusion, in combination with cisplatin (or carboplatin in case of required substitution of cisplatin in further cycles). This platinum-based chemotherapy will be administered for a maximum of 6 cycles of 3 weeks each, starting approximately 1 hour after CetuGEX™/cetuximab infusion on Day 1 of each cycle. If the CetuGEX™/cetuximab infusion is administered in the afternoon, the concomitant

platinum-based chemotherapy may be administered the next morning; however, all drugs should be given within 24 hours.

5-fluorouracil will be administered in doses of 1000 mg/m² BSA per day every 3 weeks (one cycle of cisplatin or carboplatin treatment) as continuous intravenous infusion on Days 1 to 4 of each cycle.

Cisplatin will be administered as a dose of 100 mg/m² BSA by infusion every 3 weeks, on Day 1 of each cycle, according to current standards and prescribing guidelines including hydration before and after cisplatin treatment, as required (please refer to the instructions in the corresponding SmPC [Appendix F]). In case cisplatin has to be replaced by carboplatin for toxicity reasons, Carboplatin will be administered at an area under the curve (AUC) of 5 mg/mL/min (using the Calvert formula for calculation¹²) as a 1-hour intravenous infusion every 3 weeks, on Day 1 of each cycle. As per SmPC (Appendix H), carboplatin may not be used in patients with bleeding tumors.

In case of related relevant toxicity, each compound of the chemotherapy treatment can be discontinued prior to completion of 6 cycles of chemotherapy, and patients will continue with the remaining compounds of the combination therapy. After all chemotherapy has been discontinued, irrespective if the 6 cycles are completed or discontinued prematurely for any other reason apart from progression, patients will directly enter the maintenance phase.

Single-Agent Maintenance Treatment Phase

After completion or discontinuation of chemotherapy for any other reason apart from progression, the treatment will be followed by maintenance therapy receiving CetuGEX™ alone or cetuximab alone, respectively. Single-agent maintenance therapy will be continued with unchanged dosing schedule until progression of disease or limiting toxicity.

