10.1.3 Combination Treatment Phase

During the combination treatment phase, the patients will receive the study medication (CetuGEX™ or cetuximab) in combination with chemotherapy (cisplatin and 5-FU) for a maximum of 6 cycles of combined treatment. In case of toxicity of cisplatin, carboplatin may substitute cisplatin, but after completion of the first cycle at the earliest.

During the combination treatment phase, even if the chemotherapy is delayed for any reason (e.g., see Sections 9.9.3 and 9.9.4), the IMP (CetuGEX™ or cetuximab) administration may not be withheld and needs to be continued with weekly infusions as scheduled. Additionally, all assessments related to the weekly administration of CetuGEX™/cetuximab should be performed as scheduled (see *). Only assessments relevant for the determination of whether the patient is eligible to continue the chemotherapy treatment (i.e., vital signs measurements and safety laboratory tests) have to be repeated in relation to the next administration of chemotherapy (see also Schedule of Events, Section 18.1).

If the administration of CetuGEX™ or cetuximab is skipped for any reason (see Sections 9.9.1 and 9.9.2), e.g., on Day 8, all assessments scheduled for this study visit

day are to be performed as planned (i.e., including collection of blood samples for the determination of ADA and pre-dose samples for PK).

Table 10-1 displays the ideal treatment schedule for the combination treatment phase.

Table 10-1: Ideal treatment schedule – combination treatment phase

Treatment cycle	Week	Chemotherapy ^a	IMP ^{b,c}	
1	Week 1	D1 ^d D2 – D4	D1	
	Week 2		D8	
	Week 3		D15	
2	Week 4	D1 ^d D2 – D4	D1	
	Week 5		D8	
	Week 6		D15	
3	Week 7	D1 ^d D2 – D4	D1	
	Week 8		D8	
	Week 9		D15	
4	Week 10	D1 ^d D2 – D4	D1	
	Week 11		D8	
	Week 12		D15	
5	Week 13	D1 ^d D2 – D4	D1	
	Week 14		D8	
	Week 15		D15	
6	Week 16	D1 ^d D2 – D4	D1	
	Week 17		D8	Start of maintenance phase
	Week 18		D15	

a) If the chemotherapy is delayed, the IMP (CetuGEX™ or cetuximab) administration needs to be continued with weekly infusions as scheduled.

b) Starting with the second IMP infusion (Day 8 of Cycle 1), a time window of ± 1 day will be allowed for the weekly infusions (calculated from the previous infusion).

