## **9.3 Explorative Efficacy Analysis**

### **9.3.1 Landmark Analyses**

To explore the effect of the single-agent maintenance treatment on PFS a landmark analysis will be performed based on the primary endpoint definition. The landmark will be set to the start of the maintenance therapy. Only ITT patient still at risk for progression and death at this time point will be used for the analysis. The landmark PFS will be calculated from the start of maintenance treatment using the PFSp definition accordingly. Cox regression model will be applied including the treatment effect and the stratification factors. Kaplan-Meier analyzes will be presented.

Corresponding landmark analyses will be presented for OS.

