- Any Deaths (NCI CTCAE V4.0 Grade 5 TEAEs and/or with an outcome of death)
- NCI CTCAE Grade 4, 3, 2, 1 TEAEs
- Adverse drug reactions (ADRs) (related or possibly related TEAEs)
- TEAEs leading to withdrawal of study treatment

- TEAEs leading to drug interruption or infusion rate reduction
- TEAEs requiring additional medication
- TEAEs constituting IRRs
- TEAEs marked as disease related symptoms

Incidences of TEAEs will be presented for all TEAEs and separately for the combination treatment (TEAE which occurred before first maintenance treatment) and maintenance treatment (TEAE which occurred at or after first maintenance treatment).

Incidences of TEAEs will be calculated on Preferred Term level, on System Organ Class level (SOC) and globally by treatment group. On each analysis level, a patient will be counted only once. Summaries of incidence rates (frequencies and percentages) of individual TEAEs by MedDRA SOC and Preferred Term will be prepared. Such summaries will be displayed for all TEAEs, TEAEs by maximum severity graded according to NCI-CTCAE (Version 4.03), TEAEs by strongest relationship to study treatment, and TEAEs by strongest relationship to chemotherapy. In the SOC/PT tables, events with missing grade or relationship information will be classified into the worst category. No statistical tests will be performed. In addition, separate summaries of incidence rates of IRRs and all TEAEs without IRRs by SOC and PT will be given.

IRRs will be linked to the last infusion administered before the occurrence of the IRR. Incidence rates will be calculated by SOC and PT on a per infusion basis. Moreover the first infusion per patient with a least one IRR will be identified and summarized in frequency tables.

Also, a summary of incidence rates of TEAEs by SOC and PT and of incidence rates of IRRs by FcγRIIIa-allotype subgroups (FF, FV and VV), by FcγRIIa allotypes (HH, HR, RR) the occurrence of ADAs (no/yes) and the CetuGEX™ concentration ( $C_{max}$ ) after the 3rd infusion ( $\leq$  median/ $>$ median) will be prepared.

In the AE listings all recorded AEs will be included, TEAEs will be identified by a flag variable.

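### SAP 7.2 dates maintenance from the last Day 15 infusion, which conflicts with SAP 3.1 and Protocol 9.3 when chemotherapy stops before Day 15 of a cycle

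*SAP*

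**What the plan says.** SAP 7.2 derives three antibody treatment durations, all labelled in weeks. The maintenance duration begins at the "date of first treatment administration after last Day 15 administration in combination treatment phase". The combination duration ends at the "Date of last treatment administration within a combination cycle", with no reference to Day 15. Both feed the descriptive exposure summary in SAP 8.4.

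SAP 3.1 has a patient who stops chemotherapy early, for a reason other than progression, begin maintenance at the time of stopping. Protocol 9.3 agrees: after all chemotherapy has been discontinued, "patients will directly enter the maintenance phase".

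Two other parts of the SAP need the same date:
- SAP 10.1 splits treatment-emergent adverse events (TEAEs) into combination ("TEAE which occurred before first maintenance treatment") and maintenance ("TEAE which occurred at or after first maintenance treatment").
- SAP 9.3.1 says: "The landmark will be set to the start of the maintenance therapy".

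Neither section gives a date rule or refers to SAP 7.2.

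**The concern.** The Day 15 formula is the only date rule for maintenance in the SAP. It works when the Day 15 infusion of the last chemotherapy cycle was given before chemotherapy stopped. It does not work when chemotherapy ends earlier in a cycle, or when that infusion was skipped. Protocol 9.9.1 and 9.9.2 allow infusions to be skipped for grade 3 skin toxicity.

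In those cases the rule goes back to the previous cycle's Day 15. It then takes the next infusion, a Day 1 on which chemotherapy was also scheduled, as the first maintenance infusion. The adjacent row counts the same infusion as combination treatment.

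The exposure tables would therefore contradict the SAP's own description of the phases. The larger risk is reuse. A programmer who needs a first maintenance date for the TEAE tables (14.3.1.2.2–3, 14.3.1.3.2–3 and 14.3.1.4.2–3) or for the landmark would find only this formula. If it were used, toxicity from the interrupted cycle, possibly the toxicity that ended chemotherapy, would appear in tables meant to describe the antibody alone.

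**Working it through.** The plan states no figure that depends on this rule, so there is none to reproduce. The check applies the rules to a schedule.

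**Inputs.** Cycles of 21 days, at most six (Protocol 9.3). Antibody weekly on Days 1, 8 and 15 (Protocol Table 10-1). Cycle 1 Day 1 is day 1, infusions are on schedule and chemotherapy is not delayed. The CetuGEX Day 0 dose changes none of the dates below.

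**Formulas.**
- Study day of Cycle c Day d = 21 × (c − 1) + d.
- SAP 3.1 start = first infusion after the stop.
- SAP 7.2 start, read literally = first infusion after the last Day 15 infusion given before the stop, with infusions after the stop classed as maintenance.
- Overlap = last combination infusion − SAP 7.2 start + 1, where positive.

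| Chemotherapy stop | Study day | SAP 3.1 start | SAP 7.2 start | Shift | Last combination infusion | Overlap |
|---|---|---|---|---|---|---|
| Cycle 3 Day 5 | 47 | 50 | 43 | 50 − 43 = 7 days early | 43 | 43 − 43 + 1 = 1 day |
| Cycle 3 Day 10 | 52 | 57 | 43 | 57 − 43 = 14 days early | 50 | 50 − 43 + 1 = 8 days |
| Cycle 3 Day 17 | 59 | 64 | 64 | none | 57 | none |
| Cycle 1 Day 5 | 5 | 8 | undefined | – | 1 | – |
| Cycle 1 Day 10 | 10 | 15 | undefined | – | 8 | – |

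For the first two rows, the last combination Day 15 is Cycle 2 Day 15 (21 + 15 = day 36). The next infusion is Cycle 3 Day 1 (42 + 1 = day 43). In Cycle 1 no earlier Day 15 exists.

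**Skipped infusion, no early stop.** A patient completes six cycles but skips Cycle 6 Day 15 (day 120). The last Day 15 given is Cycle 5 Day 15 (84 + 15 = day 99), so SAP 7.2 returns Cycle 6 Day 1 (day 106). The first infusion after the sixth 21-day cycle is day 127, so the start is 127 − 106 = 21 days early. The combination duration runs to Cycle 6 Day 8 (day 113), an overlap of 113 − 106 + 1 = 8 days. Had day 120 been given, both rules would return day 127.

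**The other reading.** Suppose the Day 15 infusion after the stop still counts as combination because it falls within that cycle. For both early Cycle 3 stops, SAP 7.2 then returns day 64. That is 64 − 57 = 7 or 64 − 50 = 14 days later than SAP 3.1.

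**Units.** Combination treatment through Cycle 6 Day 15 gives 120 − 1 + 1 = 120 under the formula. That is days; in weeks it is 120 / 7 = 17.1. SAP 7.2 gives conversion factors for months and years only.

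**The case against.** The strongest reply is that the Day 15 wording derives one descriptive exposure variable and does not define maintenance for the whole SAP. SAP 10.1 and 9.3.1 do not cite it, and SAP 3.1 says in words when maintenance begins. Under SAP 3.1 a toxicity that caused the stop began before the next infusion and stays in the combination tables. The phase tables carry no tests, the tables of all TEAEs do not depend on the split, and SAP 7.2 allows further derivations to be documented in the programs.

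Most of this stands. A reader might infer that the SAP counts the whole interrupted cycle, with its toxicity, as maintenance. The documents do not support that. Moving TEAEs requires the duration formula to be reused, which no section instructs. Measured against SAP 3.1, a mid-cycle stop shifts the start by 7 or 14 days, because the infusions after the stop already belong to maintenance. A stop between the Day 15 infusion and the next Day 1 gives no error, and the other reading moves the start later.

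A reader might also take "Start of maintenance phase" in Protocol Table 10-1, which appears beside Week 17 (Cycle 6 Day 8), as a contradiction for every completer. The table layout may have been broken in the PDF text, so nothing here rests on it.

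The reply does not remove the conflict within the SAP, the overlap between adjacent rows or the undefined case. If the formula is not reused, the TEAE split and the landmark still lack a date rule. The trial is open label, so a boundary first chosen in the programs could be chosen with treatment arm known.

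**Conclusion.** The point holds as a faulty derivation with limited reach. Read literally, SAP 7.2 starts maintenance 7 or 14 days early after a stop before Day 15 in Cycle 2 or later, with 1 or 8 days counted in both phases. It gives no date after a Cycle 1 stop before Day 15, and it returns Cycle 6 Day 1 for a completer who skips the last Day 15. These results assume on-schedule weekly infusions, no chemotherapy delay, and that infusions after the stop are maintenance. Under the other classification the error is 7 or 14 days in the opposite direction, so the wording does not fix one answer.

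The direct effect is on the exposure durations. Misplaced TEAEs or a shifted landmark follow only if the date is reused. A reader might want the percentage of patients affected, but the documents give neither a rate of mid-cycle stops nor event rates by cycle, so any figure would rest on assumption alone. The primary log-rank test, the 192 events and the 240 patients do not depend on this date.

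**What to change.** For analysis only, derive one maintenance start date: the first antibody infusion after the last chemotherapy agent is stopped or six cycles are completed. This follows SAP 3.1 and Protocol 9.3. Patients with no later infusion have no maintenance phase. Use the date in four places:
- as the start of the maintenance duration;
- as the end of the combination duration, which then runs to the last infusion before it;
- as the cut for the TEAE phase tables in SAP 10.1;
- as the landmark in SAP 9.3.1.

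Divide the three durations by 7. Reconcile SAP 7.2 with SAP 3.1, Protocol 9.3 and Table 10-1.

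With this date, the Cycle 3 Day 10 stop gives a combination duration of 50 − 1 + 1 = 50 days (50 / 7 = 7.1 weeks) and maintenance from day 57, with no overlap. The Cycle 1 Day 5 stop gives day 8.

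The cost is a short SAP wording change and one derived variable. There is a small downside: late toxicity of the last chemotherapy dose that begins after this date will be tabulated under maintenance, and a table footnote should say so.
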